## **VI. Study Population**

The study population for primary statistical analysis will be comprised of males and females who satisfy the inclusion/exclusion criteria outlined in this section of the protocol. In order to avoid potential selection bias, each Investigator will offer study participation to each consecutive eligible patient presenting as a candidate. Eligible candidates who express interest in study participation will be offered Informed Consent. Inclusion/Exclusion Criteria should not be evaluated until the study-specific consent form has been completed.

### **A. Inclusion Criteria**

- a. Patient must be 18 years of age or older.
- b. Patient must be eligible for an open reduction and internal fixation of the proximal femur.
- c. Patient must have an intracapsular or intertrochanteric fracture.
- d. Patient must have need for alignment, stabilization, and reduction of bone fractures.
- e. Patient must have ability and willingness to follow postoperative care instructions until healing is complete.
- f. Patient must be in good nutritional state.
- g. Patient must be able and willing to sign the IRB/EC approved informed consent.

*Note: Patients who have previously received THP Hip Fracture Plating System may be enrolled in the study if informed consent occurs prior to the end of the 6 weeks follow-up visit window.*

## B. Exclusion Criteria

- a. Patient is a prisoner.
- b. Patient is a current alcohol or drug abuser.
- c. Patient is known to be pregnant or breastfeeding.
- d. Patient has a psychiatric illness or cognitive deficit that will not allow proper informed consent.
- e. Infection.
- f. Patient conditions including bloody supply limitations, obesity or insufficient quantity or quality of bone.
- g. Patient with mental or neurologic conditions who are unwilling or incapable of following postoperative care instructions.
- h. Patient has foreign body sensitivity. Where material sensitivity is suspected or unknown, testing is to be completed prior to implantation of the device.
- i. Patient is expected to be non-compliant with recommended post-operative weight-bearing instructions.

## VII. Study Device Information

The THP Hip Fracture Plating System are left or right side specific plates designed to provide fracture fixation and stabilization of intracapsular fractures and intertrochanteric fractures by the use of telescoping lag screws. The plates are secured to the lateral aspect of the femoral shaft with either locking or non-locking cortical screws. They are intended for use in intracapsular fractures and intertrochanteric fractures of the proximal femur.

Figure 1 depicts the Hip Fracture Plates and the associated telescoping lag screws.

FIGURE 1: THP Hip Fracture Plate

The fracture plates are contoured plates made of Ti-6Al-4V titanium alloy conforming to ASTM F-136 with aTiMax™ Type II anodized surface finish. There are three (3) proximal threaded screw holes oriented 130 degrees from the plate surface to replicate a 130-degree femoral neck angle. The screw holes are threaded to allow the telescoping lag screws to lock into the plate. There are either two (2) or four (4) holes along the plate body designed for use with cortical bone screws. The screw holes in the plates are threaded, utilizing SphereLock™ Technology, to allow for the use of locking or non-locking cortical screws at the surgeons discretion.

The telescoping lag screws are 7.5mm in diameter with lengths ranging from 70mm to 130mm in 5mm increments. The head of the lag screw barrel is threaded to allow it to lock into the threads of the fracture plate. The telescoping screw portion is free to translate as much as 20mm within the barrel. The telescoping lag screws are made entirely of Ti-6Al-4V titanium alloy conforming to ASTM F-136 with a TiMax Type II anodized surface finish.

Optional limited collapse sleeves are available in 5mm, 10mm, 15mm and 20mm lengths to limit the amount of translation of the screws within the barrel. They are designed to slide into the barrel of the screw and lock into place. The use of a 5mm insert will limit the translation to 15mm whereas the use of a 15mm insert will limit the translation to 5mm. The use of the 20mm insert will make the screw virtually a non-translational (solid body) screw. The limited collapse sleeves are made of Ti-6Al-4V titanium alloy conforming to ASTM F-136 with a Type III color anodized surface finish. Figure 2 represents a 10mm limited collapse sleeve.

[figure not shown]

FIGURE 2: Limited Collapse (Sleeve 10mm)

The THP Hip Fracture Plating System plates are secured to the lateral aspect of the proximal femur by the use of 5.0mm diameter cortical screws. The cortical screws come in either a locking design or a non-locking design. The screw heads utilize a hexalobular drive design and the locking design screws have external threads incorporated into the screw head so that the screw can be locked into the threaded holes on the plate body. The head of the non-locking screws do not include the external threads. The cortical screws are made of Ti-6Al-4V ELI and

conforming to ASTM F136 with Type II color anodized surface finish. The cortical screws are available in lengths of 14mm to 60mm in 2mm increments, and from 60mm to 95mm in 5mm increments.

## VIII. Study Procedures

### A. Offer Study Participation

Study participation will be offered to each consecutive eligible patient presenting as a potential candidate for the study. Eligible candidates who express interest in study participation will be offered Informed Consent. Prior to patient involvement in the study, the patient must participate in the Informed Consent process and sign and date the IRB or EC approved Informed Consent.

### B. Informed Consent Process

For candidates that express interest, the Investigator or Designee will describe relevant study information, including the purpose, procedures, possible risks, and potential benefits associated with study participation. The Investigator or Designee will also review, along with the candidates, the Informed Consent approved by both the governing IRB or EC and the study Sponsor. Candidates shall have sufficient time to read and understand the IRB or EC approved Informed Consent and discuss whether they wish to participate in the study. Candidates will be asked to acknowledge whether all of their questions and concerns have been addressed to their satisfaction. Any questions that candidates may have will be addressed appropriately by the Investigator or Designee. Candidates will be further instructed that they are free to obtain additional information from the Investigator or Designee at any time, that they are free to decline participation, and that they are free to withdraw their consent and discontinue their participation at any time without prejudice.

After completing the Informed Consent process, candidates who agree to enter the study must sign and date the IRB or EC approved Informed Consent. The Informed Consent must be signed and dated prior to the date of the study surgery for prospective subjects. Subjects enrolled retrospectively may sign and date the Informed Consent after surgery.

A copy of the signed Informed Consent must be provided to the study subject.

The original signed Informed Consent is to be filed in the subject's medical record, study subject binder, or regulatory binder.

Study data will not be collected until the Informed Consent has been signed and dated. If the candidate does not wish to participate (does not sign and date the Informed Consent), data for that candidate will not be collected for this study.

### **C. Informed Consent / Enrollment Log**

An **Informed Consent / Enrollment Log** (Appendix C) will be maintained at the site throughout the course of the study. The purpose of the log is to provide documentation that all enrolled study subjects underwent the Informed Consent process, signed and dated the IRB or EC approved Informed Consent, and were provided with a copy of the fully executed consent with all required signatures. All candidates who sign and date the approved Informed Consent for the study must be entered in the log. If a subject signs and dates additional Informed Consent(s) after enrollment (e.g., due to a protocol amendment, protocol revisions, etc.), subsequent signings will also be recorded in the log. The Informed Consent/Enrollment Log will be filed in the site Regulatory Binder for the study.

### **D. Subject Enrollment**

Once the Informed Consent has been signed and dated by the subject, the subject will be considered enrolled in the study. A unique case identification number (Case ID) will be assigned to each participating subject/femur (bilateral subjects will be assigned a unique case ID number for each femur). This unique case ID number will be used throughout the study for identification. Case ID numbers will be assigned consecutively in ascending order per site, with the starting number for a given site defined by the Sponsor.

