## II. Data Collection Overview

The following table indicates the necessary case report forms to be completed at the given time point:

Form Name	Enrollment	Operative	Discharge Assessment	1 to 6 Weeks Post-op (+14 days)	3 Months Post-op ( $\pm 30$ days)	6 Months Post-op ( $\pm 60$ days)	1 Year Post-op ( $\pm 90$ days)	Revision
Enrollment Form	X							
Demographic Evaluation	X							
Operative Record		X						
Postoperative Discharge Assessment			X					
VAS Pain				•	•	•	•	
EQ-5D-5L				•	•	•	•	
FIX-IT				X	X	X	X	
X-rays	X	X	X	X	X	X	X	X
Postoperative Follow-up Evaluation				X	X	X	X	
Study Completion		*	*	*	*	*	*	X
**Adverse Event (Complication)	*	*	*	*	*	*	*	X
Protocol Deviation	*	*	*	*	*	*	*	*
Physician Radiographic Assessment (Including RUSH)				*♦	*♦	*♦	*♦	*♦
Explant Device			X	X	X	X	X	X

X Completed by Investigator or Designee (required)
 
 
• Completed by Patient
 
* Completed by Investigator or Designee (as applicable)
 
♦ Independent radiographic review may be performed by Sponsor's designee if requested by the Sponsor.
 
 
** If device related Adverse Event occurs, a Product Experience Report (PER) must be completed and sent to the sponsor as well and include the Operative Report (index and revision) and Radiographs (immediate post-op, all follow-up visits, and pre-revision).
								

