## V. Study Design

This is a prospective, multicenter, non-controlled clinical study designed to facilitate the collection and evaluation of pain, function, quality of life, radiographic assessment, and adverse event data. A maximum of 10 sites will contribute to this study to enroll a study maximum of 190 subjects. Enrollment per site will not exceed 57 subjects (30% of the total sample). Each Investigator will be skilled in femur fracture treatment and experienced implanting the devices included in this study, as determined by the Sponsor.

Due to the different historical revision rates for intertrochanteric fractures (~7%) and neck fractures (~20%), study enrollment will be split between the two groups to maintain the integrity of the sample size with an expectant lost to follow-up rate of 15%.

Intertrochanteric fractures will be limited to a maximum of 89 enrolled subjects and intracapsular fractures will be limited to a maximum of 101 enrolled subjects. This will provide enough evaluable data for both indications to show the necessary statistical improvement from the historical revision rates.

Each Principal Investigator will be responsible for obtaining Institutional Review Board (IRB) or Ethics Committee (EC) approval as required prior to conducting the study. In order to avoid potential selection bias, each Investigator will offer study participation to each consecutive eligible patient presenting as a candidate for hip fracture repair using the commercially available (FDA cleared) THP Hip Fracture Plating System. Eligible candidates who express interest in study participation will be offered Informed Consent. All potential study subjects will be required to participate in the Informed Consent process and will not be considered enrolled in the study until the candidate has signed and dated the IRB/EC approved patient Informed Consent. Study data cannot be collected until the candidate has completed the Informed Consent process and signed and dated the IRB or EC approved Informed Consent.

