**B. Clinical Data Collection/Submission**

**1. Summary of Case Report Form Data Collection**

- a. Study data will be collected on source documents which may include study-specific worksheets provided by the Sponsor. For subjects having bilateral proximal femur fracture treatment, separate case report forms must be completed for each operative side.
- b. The following source document/CRF completion guidelines should be followed:
  - i. Complete carefully and accurately.
  - ii. Complete header information consistently across all case report forms for each individual study subject (when study-specific CRFs are used).
  - iii. Be sure that data on the source documents match that which is entered through the electronic data capture (EDC) system
  - iv. Use the study subject's unique Case ID number assigned as instructed. Do not provide information that is not requested on the CRFs.
  - v. Ensure that all fields are completed. For fields completed by the subject, efforts should be made to obtain any missing responses prior to the subject completing their visit.

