**D. Management of Incurrent Events**

**1. Failure to Obtain Informed Consent**

Study data will not be collected until the Informed Consent has been

signed and dated by the candidate. If a candidate does not wish to participate (does not sign and date the Informed Consent), data for that candidate will not be collected for this study.

2. Adverse Events

An adverse event is any unfavorable or unintended sign, symptom, or disease that impacts the subject. Adverse event is synonymous with complication or medical event.

See Section IX, Subsection E of this protocol for additional information regarding adverse event classifications. Femur related, serious, and unanticipated events are required to be reported on the **Adverse Event Report** case report form. The completed **Adverse Event Report** case report form must be submitted to the Sponsor in a timely manner. The Investigator or Designee will also promptly provide the Sponsor with any additional requested information required for the Sponsor to comply with regulatory requirements. If applicable per their reporting requirements, the Investigator or Designee will also report applicable adverse event(s) to their IRB or EC.

3. Revision

In the event that removal of one or more of the study related components is necessary (due to complication), the Investigator will determine the best treatment and/or revision method for the subject. Once the revision surgery has been completed, the Investigator or qualified Designee must complete an **Adverse Event Report** case report form as well as a **Study Completion** case report form terminating the subject from the study.

4. Investigator Withdrawal

The Investigator can choose to withdraw a subject from the study if the subject no longer meets study inclusion/exclusion criteria. The reason for the Investigator's withdrawal of the subject must be documented on the **Study Completion** case report form.

5. Subject Withdrawal

Study subjects may choose to withdraw from the study at any time, for any reason. If possible, a final evaluation will be completed for any subject who no longer wishes to participate in the study. The reason for the subject withdrawal must be documented on the **Study Completion** case report form.

6. Lost to Follow-up

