### **B. Sample Size**

Due to the different historical revision rates for intertrochanteric fractures (~7%) and intracapsular fractures (~20%), study enrollment will be split between the two groups to maintain the integrity of the sample size with an expectant lost to follow-up rate of 15%. Intertrochanteric fractures will be limited to a maximum of 89 enrolled subjects and intracapsular fractures will be limited to a maximum of 101 enrolled subjects. This will provide enough evaluable data for both indications to show the necessary statistical improvement from the historical revision rates. The assumed revision rate of the THP Hip Fracture Plating System is 15% for intracapsular fractures and 5% for intertrochanteric fractures with a non-inferiority margin of 8%.

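### Bilateral subjects are recorded per femur but sized and terminated per subject, so read literally a revision on one side ends follow-up of the other, and no analysis unit is named

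*Combined protocol and SAP*

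**What the plan says.** **Records are kept by femur.** Section VIII.D (Subject Enrollment) states that "bilateral subjects will be assigned a unique case ID number for each femur", and that number identifies the case throughout the study. Section IX.B.1 adds: "For subjects having bilateral proximal femur fracture treatment, separate case report forms must be completed for each operative side". It makes no exception for the forms that the table in Section II marks "Completed by Patient", which are VAS Pain and EQ-5D-5L.

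**The sample is counted in subjects.** Section V plans "to enroll a study maximum of 190 subjects". Section XI.B says "Intertrochanteric fractures will be limited to a maximum of 89 enrolled subjects" and "intracapsular fractures will be limited to a maximum of 101 enrolled subjects". The site cap of 57 in Section V is in subjects too.

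**Follow-up ends by subject.** After a revision, Section IX.D.3 requires an adverse event form and a Study Completion "case report form terminating the subject from the study". Sections VIII.I and IX.D.8 carry the same subject-level rule and apply it even to partial removal, such as a single screw.

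**The analysis unit is not stated.** Section XI.A provides counts, percentages, means, 95% confidence intervals and Kaplan-Meier estimates. Section XI does not say whether the unit is the subject or the femur, has no rule for bilateral subjects and gives no expected number of them.

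**The concern.** The protocol provides for bilateral subjects in its data collection but not in its statistics. Two things follow.

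The first concerns the primary endpoint, revision at 12 months (Section IV). On the literal wording, removing a component from one femur stops data collection on the other. That femur leaves the risk set because its pair failed. Kaplan-Meier assumes that a censored femur has the same future risk as those still followed. If the two hips of one person share bone quality, gait or surgeon, the censored femur is at higher risk and the revision rate is understated.

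The second is conditional. If the dataset were analysed with one row per Case ID, a bilateral subject's EQ-5D-5L, death or readmission would enter twice, and ordinary intervals would treat two correlated femurs as independent.

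A smaller matter is the denominator. A subject with one intracapsular and one intertrochanteric fracture has no stated place under the two caps.

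**Working it through.** **1. The plan's own sample size.** Inputs from Section XI.B: historical rates of 7% and 20%, assumed device rates of 5% and 15%, margin 8%, loss 15%. Alpha and power are not stated; one-sided 0.05 and 90% power are assumed because they come closest to both caps. The one-sample formula with bound pb = historical rate + 0.08 is

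n = [1.645·√(pb(1−pb)) + 1.282·√(p1(1−p1))]² / (pb − p1)²

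- Intertrochanteric (pb 0.15, p1 0.05): n = 75.1; 75.1/0.85 = 88.4, so 89 (stated: 89).
- Intracapsular (pb 0.28, p1 0.15): n = 84.7; 84.7/0.85 = 99.6, so 100 (stated: 101).

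The caps are therefore consistent with a calculation that treats each unit as one independent observation.

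**2. Interval width if Case IDs were analysed as independent.** Let b be the number of bilateral subjects among 190 and ρ the within-person correlation. Neither is in the documents, so both are assumed. The ratio of true to naive variance is

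DE = [(190 − b) + 2b(1 + ρ)] / (190 + b) = 1 + 2bρ/(190 + b)

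and the interval should be √DE − 1 wider.

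| b | DE, ρ = 0.5 | wider by | DE, ρ = 1 | wider by |
|---|---|---|---|---|
| 2 | 1.0104 | 0.5% | 1.0208 | 1.0% |
| 5 | 1.0256 | 1.3% | 1.0513 | 2.5% |
| 10 | 1.0500 | 2.5% | 1.1000 | 4.9% |
| 19 | 1.0909 | 4.4% | 1.1818 | 8.7% |

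The ρ = 1 columns describe a duplicated whole-person score. At b = 19 and ρ = 1, a nominal 95% interval covers about 92.9%. The formula pools both fracture groups. A subject with one femur in each group adds no clustering to either group's estimate.

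**3. Planned precision.** Take 5% of subjects bilateral, ρ = 0.5, so DE = 1 + 2(0.05)(0.5)/1.05 = 1.0476.

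- If 89 counts subjects: 89 × 0.85 = 75.65 evaluable subjects give 75.65 × 1.05 = 79.4 femurs, worth 79.4/1.0476 = 75.8 independent ones. Nothing is lost. At ρ = 1 (DE 1.0952) they are worth 72.5.
- If the 89 and 101 places were filled by Case IDs: 75.65/1.0476 = 72.2, and 85.85/1.0476 = 81.9.

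**4. Size of the cut-off.** Use the plan's device rates. With independent femurs, the chance that a bilateral subject has any revision is 1 − 0.95² = 0.0975 (both intertrochanteric) or 1 − 0.85² = 0.2775 (both intracapsular). Among 2 to 5 bilateral subjects that is 0.2 to 1.4 subjects, and among 19 it is 1.9 to 5.3. Positive correlation lowers these counts, and each such subject loses follow-up on at most one femur.

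The femurs cut off are not typical. At ρ = 0.5 for 12-month status, the chance of revision given that the pair is revised is p + ρ(1 − p): 0.05 + 0.475 = 0.525, or 0.15 + 0.425 = 0.575, against 0.05 and 0.15 overall.

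The second revisions that could go unseen number at most b[p² + ρp(1 − p)]. With all bilateral subjects intracapsular and ρ = 0.5, this is 0.08625b: 0.43 for b = 5 and 1.64 for b = 19. As a crude share of femurs that is 0.43/106 = 0.4 and 1.64/120 = 1.4 percentage points. With all of them intertrochanteric it is 0.02625b: 0.13/94 = 0.1 and 0.50/108 = 0.5 points. These are ceilings, because two femurs revised together lose nothing.

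**The case against.** The strongest reply is that the plan never says Case IDs will be analysed as independent records. Section VIII.D gives the number as an identifier only. A reader might infer that scores will be double counted and that the reported intervals will be too narrow. The documents do not support that as a fact: it needs bilateral subjects to enrol, an analysis by Case ID, and no allowance for correlation. Nor does duplication apply to every measure. RUSH is specific to a femur, and VAS Pain or FIX-IT may be recorded per side; the forms themselves are not in the text. This reply stands, so the interval and double-counting points are conditional.

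The second reply is that Study Completion is itself a case report form, that forms are per side, and that Section VIII.D treats subject and femur as one unit when it assigns the Case ID. The form could then be read as closing one side only. That reading is possible, but it goes against the wording of three sections. The ambiguity is a reason to reconcile them.

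A reader might also infer that the study is underpowered because of this. The documents do not show it. With caps in subjects, as written, second femurs are extra data and planned precision is essentially kept at a correlation of 0.5.

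Finally, the bilateral count may be very small. That stands, and it limits the size of the whole point.

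**Conclusion.** The point holds in a limited form and is minor. Established from the text: femur-level identification and forms, subject-level sizing, a subject-level termination rule in three places, and no analysis unit. Read literally, that rule cuts off an unrevised second femur's primary endpoint because of its pair, and this can bias revision downward if outcomes within a person are positively correlated. Under the assumptions above, the crude shortfall is at most about 0.1 to 0.4 percentage points with 5 bilateral subjects and 0.5 to 1.4 points with 19.

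The effect on intervals depends on the analysis being by Case ID: 0.5% to 4.4% at correlation 0.5 and 1.0% to 8.7% at correlation 1, for 2 to 19 bilateral subjects. Both the counts and the correlations are assumptions. These figures overstate the effect within a group wherever a subject's two femurs belong to different fracture groups.

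**What to change.** - **Sections VIII.I, IX.D.3 and IX.D.8:** reconcile all three with the per-femur Case ID. Study Completion after a revision should close only the revised femur's Case ID, and data collection on the other femur should continue to 12 months. Changing IX.D.3 alone would leave it in conflict with the other two.
- **Section XI.A, whole-person measures:** count EQ-5D-5L, death and readmission once per subject.
- **Section XI.A, femur-level rates and Kaplan-Meier:** analyse within each fracture group with a variance clustered on subject (robust). The alternative is one index femur per subject, defined in advance, including for both sides treated together. Clustering keeps every femur; the index-femur rule is simpler but drops some, and may take a valid observation from one group when the two femurs differ in fracture type.
- **Section XI.B:** state that 89, 101 and 190 count subjects, and how a subject with one fracture of each type is counted.

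The cost is slightly wider intervals, a little extra follow-up data and a protocol amendment, with ethics approval where required (Section IX.D.9). The change concerns data collection and analysis only.
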